**Project Summary** 

Ethics Review Number of Wuhan Sports University School of Medicine:2023102

Chronic Ankle Instability (CAI) is a common sports injury disorder. Athletes also suffer from

patellofemoral pain in their daily lives and training. Instrument Assisted Soft Tissue Mobilization

(IASTM) is a physical therapy technique that uses specially designed tools such as metal or plastic

scraping boards to assist in handling soft tissue problems. Mainly used in rehabilitation medicine,

sports medicine, and plastic surgery, it is used to handle tension, adhesion, pain, and motor

dysfunction of muscles, fascia, and tendons [25, 26, 27]. Blood Flow Restriction Training (BFRT)

is a special training technique aimed at limiting blood flow through the use of cuffs or elastic

bands on the limbs, in order to promote muscle growth and improve strength

Therefore, in order to further optimize the rehabilitation process of CAI, this study designed a

comprehensive rehabilitation training program that combines blood flow restriction training

(BFRT) with ankle balance training, ankle peripheral reinforcement training, and IASTM physical

release. BFRT was chosen because it has the adaptability to generate muscle strength at lower

loads, providing a relatively low-risk approach for rehabilitation. The combination of ankle

balance training and reinforcement training, as well as the physical release of IASTM, is expected

to play a synergistic role in promoting the rehabilitation process. By comparing conventional

balance training with pure BFRT training, this study aims to evaluate the effect of BFRT assisted

rehabilitation on ankle rehabilitation of sports dance athletes, providing new theoretical and

empirical support for the rehabilitation field. Through in-depth research, it is expected to provide

more effective and comprehensive rehabilitation plans for sports dance athletes, improve their

rehabilitation speed and effectiveness, and better safeguard their health and career.

**Basic information** 

Agreement Title: The effect of blood flow restriction training on chronic ankle instability

symptoms in sports dance athletes

Acceptance number: 2023102

Date; 2023.11.20-2023.12.30

The guarantor; [name], Wuhan Sports College, Hubei Province, China

Telephone; [name]

Clinical laboratory; Wuhan Sports Institute Sports Rehabilitation Laboratory and Wuhan Sports

Institute National Fitness Center

Sports dance, also known as international standard dance, is divided into two series: Latin

and Modern. In this high-intensity sport, athletes often face the risk of various sports injuries,

among which chronic ankle instability (CAI) is a common and significant problem in dance sports

[1,2]. Repeated sprains during exercise and long-term ankle joint dysfunction are important factors

leading to CAI [3,4]. Its main feature is the reduced stability of the ankle joint, which increases the

risk of ankle re sprains for patients during walking, exercise, or other activities [4,5]. For sports

dancers, the ankle is one of the joints that bear the greatest pressure during exercise, and its

complex structure and frequent exercise requirements make the ankle joint more susceptible to

injury. The injury of the ankle joint is highly correlated with the characteristics of sports dance

projects. Due to the need for sports dance athletes to perform high-frequency and difficult

movements, the ankle is in a constantly changing load state. This sport characteristic puts the

ankle at a high risk of injury [6]. Especially in dance events that require frequent changes in

direction and jumping movements, ankle sprains, ligament strains, and other forms of injury are

very common [7]. Secondly, in addition to the unpredictable demands of dance movements on the

ankle, some high demand movements may lead to ankle injuries in unstable states. Continuous

high-intensity dance training and performance may increase the risk of ankle muscle fatigue and

injury [8]. Ankle joint injury may not only affect the athletic performance of athletes, but also lead

to delays in the rehabilitation process, which can have adverse effects on the athlete's career. After

the rest symptoms disappear, the muscles around the ankle joint may become weak due to trauma

or inadequate recovery, including the gastrocnemius and tibialis anterior muscles around the ankle. Muscle weakness or incomplete ligament healing can lead to insufficient joint support, resulting in loss of ankle stability, which is also an important factor in inducing CAI [9,10]. Moreover, the ability of nerves to control muscle movement may be affected, leading to inadequate muscle coordination and increasing the risk of ankle instability [11]. Therefore, strengthening training for the strength and stability of the ankle joint after rehabilitation is particularly important.

Blood Flow Restriction Training (BFRT) is a special training technique aimed at limiting blood flow by using cuffs or elastic bands on the limbs to promote muscle growth and improve strength [13]. BFRT was originally designed for rehabilitation injured athletes because it can improve muscle strength while reducing load, helping to avoid further injuries during the rehabilitation process [14]. But as research deepens, it is gradually being applied to a wider range of fitness and training fields [15,16]. One major advantage of BFRT is that it allows for efficient training under relatively light loads, reducing the burden on joints and tendons, making it suitable for people who find it difficult to withstand high-intensity training due to injuries or other reasons [14]. Meanwhile, BFRT also has the characteristic of achieving muscle growth and strength growth in a short period of time, and it is considered a time-saving training method [14]. BFRT can not only be used for strength training, but also for rehabilitation, improving endurance, and improving sports performance, making it have potential applications in various fields [15]. In rehabilitation training, it can be applied to multiple body parts to promote the recovery of injured areas and improve muscle strength, including; Direct effects on limb muscle groups and elbow and knee joints, indirect effects on shoulders, hips, and buttocks [17, 18, 19, 20], among which studies have shown that BFRT has an activating effect on the calf muscle group of CAI athletes. Under low load resistance exercise, the oxygen saturation of the calf muscle group is significantly reduced, and the muscle fatigue perception score is significantly improved, which has an impact on the strength of the lower limbs of CAI patients There is a promoting effect in terms of functionality and other aspects [21, 22, 23].

Instrument Assisted Soft Tissue Mobilization (IASTM) is a physical therapy technique that utilizes specially designed tools (such as metal or plastic scraping boards) to assist in the treatment of soft tissue problems [24]. Mainly used in rehabilitation medicine, sports medicine, and plastic surgery, it is used to handle tension, adhesion, pain, and motor dysfunction of muscles, fascia, and

tendons [25, 26, 27]. The edge design of IASTM special tools can loosen adhesions in tissues, improving their elasticity and plasticity. Regulating pathological areas through neural pathways, reducing pain and improving neurological function [28]. And different types of treatment tools improve the accuracy of treatment, promote blood circulation, accelerate the rehabilitation process, improve tissue elasticity, expand joint range of motion, and have lower risks and complications compared to invasive surgery [29,30,31]. Studies have shown that IASTM can significantly improve lower limb joint function, reduce pain, and increase range of motion [19, 28].

Therefore, in order to further optimize the rehabilitation process of CAI, this study designed a comprehensive rehabilitation training program that combines blood flow restriction training (BFRT) with ankle balance training, ankle peripheral reinforcement training, and IASTM physical release. BFRT was chosen because it has the adaptability to generate muscle strength at lower loads, providing a relatively low-risk approach for rehabilitation. The combination of ankle balance training and reinforcement training, as well as the physical release of IASTM, is expected to play a synergistic role in promoting the rehabilitation process. Through in-depth research, it is expected to provide more effective and comprehensive rehabilitation plans for sports dance athletes, improve their rehabilitation speed and effectiveness, and better safeguard their health and career.

# **Research Objective**

Through experimental observation of exercise intervention (blood flow restriction training

combined with low load ankle muscle strength training and balance training) combined with instrument tool therapy (Instrument Soft Tissue Release Technique, IASTM), the intervention effect on ankle function, strength, and joint range of motion of sports dance athletes with ankle instability was observed.

## Research process and methods

Method; Select 30-45 subjects with unstable, restricted, or uncomfortable ankle joints as observation subjects, and randomly divide them into ankle joint blood flow restriction training combined with IASTM group (n=10-15), ankle joint blood flow restriction training alone (n=10-15), and traditional ankle strength training (n=10-15). The intervention lasted for 4-6 weeks, once a week. Cumberland ankle instability assessment, FAAM ankle function assessment score, and ankle range of motion measurement were performed at three time points before intervention, after the first intervention, and after 4 weeks/6 weeks of intervention for the three groups. The ankle strength test was only compared and analyzed at two time points before and after intervention.

Process: This study is divided into three stages: pre intervention stage, post initial intervention stage, and post intervention stage. In the pre intervention stage, researchers will conduct preliminary evaluations and data statistics on subjects, including Cumberland ankle instability assessment, FAAM ankle function assessment score, and ankle range of motion measurement. During the intervention phase, participants from each group will undergo a 6-week exercise intervention, with a training frequency of 2 sessions per week and each session lasting 20-30 minutes. During BFRT exercise, a cuff will be wrapped around the proximal one-third of the upper limb of the subject to improve muscle strength and endurance by restricting blood flow. In this state, corresponding ankle training movements (stability training, ankle peripheral muscle group training) will be completed.

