**Table 1 Inclusion and Exclusion Criteria** 

Standard	Inclusion Criteria	Exclusion Criteria	
Age	118-35 years old	under 18 years old or above 35 years o	
Course Of	Suffering from chronic ankle instability	Acute ankle injury or no joint injury	
Disease	symptoms that last for at least 3 months		
CAIT score	The CAIT score is 24 points or less.	CAIT score above 24 points	
Functional	Two or more tests tested positive for ankle	Failed ankle function screening	
screening	joint function screening before the		
	experiment		
Structural	No structural joint lesions or congenital	Structural lesions or congenital ankle	
inspection	ankle deformities,	deformities present in the ankle joint	
Medical	Have not undergone ankle surgery or have	Have undergone ankle surgery or have obvious	
History	external injuries	injuries or wounds	
Health	No serious heart, lung, nervous system or	Serious heart, lung, nervous system or other	
Condition	other systemic diseases	systemic diseases	
Agree to	Limited athletic ability, unable to complete	Disagree to participate in the study, or inability	
participate in	research tasks	to understand and comply with the research	
research		protocol	

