# **Project Deadline**

20/10/2023

Recruitment end date

19/011/2023

Overall test start date

20/11/2023

Overall Trial End Date 30/12/2023

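### The plan names no restriction on allocation and no baseline covariate; if allocation is unrestricted, there is a 36–50% chance that some pair of the three arms starts 0.5 SD or more apart on CAIT, which is cheap to prevent

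*Combined protocol and SAP*

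**What the plan says.** Research process and methods sets a total of 30 to 45 people in three arms. Its whole description of allocation is that the investigators will "randomly divide them into ankle joint blood flow restriction training combined with IASTM group (n=10-15"). The other two arms, BFRT alone and traditional strength training, have the same size range of 10 to 15. The Chinese text of the same section says the same. Neither version describes how the sequence is produced or whether it is restricted.

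Three other places bear on the point:
- **Calendar.** Project Deadline lists the "Recruitment end date" as 19 November 2023 and the "Overall test start date" as 20 November 2023. Basic information agrees on the start: "2023.11.20-2023.12.30".
- **CAIT before allocation.** Table 1 requires that "The CAIT score is 24 points or less", so every enrolled participant has a score at entry. CAIT is also an outcome measured before treatment: "In the pre intervention stage, researchers will conduct preliminary evaluations and data statistics on subjects, including Cumberland ankle instability assessment".
- **Analysis.** The Statistical analysis section plans repeated measures ANOVA for function and range of motion, and paired t-tests for strength. It mentions no baseline covariate or stratification factor.

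**The concern.** With 10 to 15 people per arm, an unrestricted random split often produces arms that differ visibly in starting severity. An arm that happens to start worse tends to improve more through regression to the mean. A comparison of changes without baseline adjustment then credits or debits part of that to treatment.

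Most small trials enrol one person at a time and cannot match the whole cohort. By the plan's own calendar this one can: the list is complete, with an entry CAIT score for each person, before the first session. The plan makes no stated use of that, either in allocation or in analysis.

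**Working it through.** The plan gives no sample-size calculation or imbalance figure, so there is no stated number to reproduce.

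**Inputs.** Three arms of n = 10 to 15 (Research process and methods). Assumed: unrestricted allocation, and approximately normal scores for the closed-form results. Results are in SD units, so no CAIT SD is needed; the documents give none.

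**1. Spread of the baseline difference between two arms.** SD of difference = √(2/n).
- n = 10: √0.200 = 0.447 SD
- n = 15: √0.133 = 0.365 SD

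**2. One pre-named pair at least 0.5 SD apart.** P = 2 × [1 − Φ(0.5/√(2/n))].
- n = 10: 0.5/0.447 = 1.118, P = 26.4%
- n = 15: 0.5/0.365 = 1.369, P = 17.1%

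**3. At least one of the three pairs at least 0.5 SD apart.** This is the upper tail of the studentized range for 3 means with infinite df, at q = 0.5√n.
- n = 10: q = 1.581, P = 50.3%
- n = 12: q = 1.732, P = 43.8%
- n = 15: q = 1.936, P = 35.7%

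Unequal arms give 46.0% (10/10/15) and 41.2% (10/15/15). Simulation with integer scores truncated at 24 (assumed mean 19 and SD 4 before truncation) gives 49–52% at n = 10 and about 37% at n = 15.

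**4. Effect of a 0.5 SD gap on an unadjusted change comparison.** With equal SDs, baseline–follow-up correlation r and no treatment effect, the expected follow-up gap is r × 0.5. The change comparison therefore shifts by (1 − r) × 0.5.
- r = 0.7: 0.15 SD
- r = 0.4: 0.30 SD

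These r values are assumed. The standard error of a change difference is √(2(1 − r)) × √(2/n), which gives:

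| | n = 10 | n = 15 |
|---|---|---|
| r = 0.7 | 0.15/0.346 = 0.43 SE | 0.15/0.283 = 0.53 SE |
| r = 0.4 | 0.30/0.490 = 0.61 SE | 0.30/0.400 = 0.75 SE |

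**5. What restriction achieves.**
- Two strata split at the median, balanced within each: the chance in step 3 falls to about 14–16% (n = 10) and 6–7% (n = 15).
- Sorted by CAIT and randomised within consecutive triples: SD of the pairwise difference is 0.10 (n = 10) and 0.06 (n = 15), and the chance in step 3 is below 0.01%.

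**6. What matching adds once baseline is a covariate.** Chance imbalance inflates the adjusted variance of a pairwise contrast by about 1/(3(n − 1) − 2) on average.
- n = 10: 1/25 = 4.0%
- n = 15: 1/40 = 2.5%

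Simulation gave 4.0% and 2.6%, against 0.2% and 0.1% with matched triples. Matching therefore saves about 2.5–4% of variance beyond adjustment.

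**The case against.** **The method is inferred from silence.** This stands. A reader might infer that the plan has chosen simple randomisation. The documents do not say so; they describe no restriction and rule none out. The probabilities above are conditional on unrestricted allocation. If a restriction was intended, it still needs to be written down.

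**Chance imbalance is not bias.** This stands too. A reader might infer that the trial's comparisons are biased. Randomised comparisons are unbiased on average, and ordinary standard errors already allow for baseline variation. The 0.15–0.30 SD shift applies only given a 0.5 SD gap, at the assumed correlations, and to a between-arm comparison of changes. The Statistical analysis section does not say which ANOVA effect will be tested.

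**The any-pair figure is the least favourable one.** Partly stands. For a single named contrast the figure is 17–26%, and 0.5 SD is a chosen threshold. But the plan names no primary contrast, so both figures belong here.

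**Adjustment does most of the work.** This stands (step 6) and sets the order of the fixes.

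**Matching on CAIT protects mainly CAIT.** This stands. No primary outcome is named. FAAM, range of motion and strength are balanced only as far as they correlate with CAIT, and the documents give no correlations.

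**Arm size.** A reader might infer that unequal arms are planned. The total of 30–45 is exactly 3 × 10 to 3 × 15, so the range more naturally reflects an uncertain total. Even 10 versus 15 costs little: √(1/10 + 1/15) = 0.408, against √(2/12.5) = 0.400 for equal arms, or 2% in standard error.

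**The calendar is tight.** Partly stands. There is one day between closing recruitment and starting, with no stated window for baseline testing, and the plan does not say that the entry and pre-intervention CAIT are the same measurement. Sorting on the entry score, which eligibility already requires, avoids the difficulty.

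**Conclusion.** The point holds as a low-cost improvement to an under-described allocation and an unadjusted analysis. It is not a threat to validity. If allocation is unrestricted, some pair of arms will start at least 0.5 SD apart on CAIT in 36–50% of such trials, and one pre-named pair in 17–26%. Given such a gap, an unadjusted change comparison moves by 0.15–0.30 SD, or roughly 0.4 to 0.75 of its standard error, for r between 0.7 and 0.4. Baseline adjustment removes most of this. Matching then brings near-equal starting CAIT, arms equal to within one participant, and a further 2.5–4% of variance.

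The imbalance probabilities rest on arithmetic and the unrestricted-allocation assumption. The size of the shift also rests on the assumed correlations.

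**What to change.** **First, in Statistical analysis:** state that arms are compared on follow-up values, with each outcome's own baseline value as a covariate (pre-intervention CAIT for CAIT, and likewise for FAAM, range of motion and strength). Baseline is then a covariate and not also one of the responses. This uses data already collected and costs nothing.

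**Second, in Research process and methods:** replace the bare statement of random division with wording such as: *After recruitment closes, the list is locked and sorted by entry CAIT score. Consecutive sets of three are formed, and the three arms are allocated at random within each set in a single computer run with a saved seed. If the last set is incomplete, its members are allocated at random to different arms.* Reflect this in the analysis by including entry CAIT (or the set) in the model.

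**Cost:** a few lines of code, with no extra visits, staff or data. Allocation has to wait until the list is closed, which the stated dates allow because entry scores exist by then. Balance on outcomes other than CAIT remains limited by their correlation with it.

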#### Research indicators

# Cumberland ankle instability questionnaire

The Cumberland Ankle Instability Tool (CAIT) [42] assessed patients' perception of ankle instability, including the frequency, intensity, and impact of symptoms. CAIT typically includes a specific range of questions, each of which may have different scores. The total score is usually between 0 and 30 points

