#### **FAAM Ankle Function Assessment Questionnaire**

Foot and Ankle Ability Measure (FAAM) is a scale used to evaluate ankle joint function, which includes questions about pain, function, and quality of life, and can be used to assess the overall condition of patients with ankle instability. The functional score includes two types of assessments: the functional level of daily life (FAAM-ADL) and the functional level of physical activity (FAAM-SPORT). The score range is usually from 0 to 100, where 100 represents completely normal ankle joint function, and 0 represents extreme restriction or complete inability to use the ankle joint.

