## Statistical analysis

This study used SPSS 26.0 statistical software for data reading, testing, and statistical analysis.

The general information of the subjects is analyzed using an independent sample t-test. The measurement data conforms to a normal distribution. Because there are three time points (pre intervention, first intervention, and 6-week intervention) in the experimental data for measuring ankle joint function indicators and range of motion indicators, repeated measures analysis of variance is used for data statistics and analysis. Ankle joint strength was only measured at two time points (before intervention and after 6 weeks of intervention), and the data was only analyzed using paired t-tests. P<0.05 is a significant difference with statistical significance.

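### The only intermediate CAIT and FAAM scores are taken after a single session, where they can hardly show lasting change, and no between-group baseline-to-end comparison is named to keep that visit from driving the result

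*Combined protocol and SAP*

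**What the plan says.** Research process and methods (English text, with the same content in Chinese) states that "Cumberland ankle instability assessment, FAAM ankle function assessment score, and ankle range of motion measurement were performed at three time points". It gives these as "three time points before intervention, after the first intervention, and after 4 weeks/6 weeks of intervention for the three groups". It names the stages as "pre intervention stage, post initial intervention stage, and post intervention stage". No interval in minutes, hours or days is attached to the middle one. The Process paragraph there describes 6 weeks of training "with a training frequency of 2 sessions per week and each session lasting 20-30 minutes"; the Method paragraph of the same section gives once a week for 4-6 weeks. Strength is measured only before and after.

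The instruments are described in their own sections. CAIT "assessed patients' perception of ankle instability, including the frequency, intensity, and impact of symptoms". FAAM is scored for "the functional level of daily life (FAAM-ADL) and the functional level of physical activity (FAAM-SPORT", and its items are said to include pain and quality of life. No recall period is given for either questionnaire.

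Statistical analysis justifies a repeated-measures ANOVA because "there are three time points (pre intervention, first intervention, and 6-week intervention" are available. It names no main time point, no between-group contrast and no model term of interest. Blinding is not mentioned anywhere.

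**The concern.** Range of motion can plausibly change within a session, and the Experimental Group section says the soft-tissue release is meant to restore it. A reading after session 1 makes sense for that measure. CAIT and FAAM are different: how often an ankle feels unstable, or how well someone manages daily life and sport, can be re-judged only after some daily life and sport. After one session, any movement in the score is more likely to come from something short-lived. Participants can see whether they are given a cuff or treated with blades, so such influences need not be equal across arms.

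Two things are at stake. First, a passing difference at the middle visit could be reported as a group-by-time effect on instability or function when the arms do not differ at the end. Second, the one intermediate questionnaire is spent where it says little about how recovery proceeds.

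**Working it through.** The plan gives no power calculation, effect size, SD or correlation, so there is no figure of its own to reproduce.

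**Step 1. How much treatment precedes the middle visit.** Sessions = weeks × frequency.
- Process text: 6 × 2 = 12 sessions, so 1/12 = 8.3% delivered.
- Method text: 4 × 1 = 4 to 6 × 1 = 6 sessions, so 1/4 = 25% to 1/6 = 16.7% delivered.

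**Step 2. How much of the course then goes unobserved.** If the middle visit is on the day of session 1, essentially all of it. The latest timing taken here is just before session 2, which is 7/2 = 3.5 days or 7/1 = 7 days later. The unobserved share is then 1 − 7/28 = 75% (4 weeks, weekly), 1 − 7/42 = 83% (6 weeks, weekly) or 1 − 3.5/42 = 92% (6 weeks, twice weekly).

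**Step 3. Can the middle visit alone make the group-by-time test significant?** The plan does not name the ANOVA term; group-by-time is taken as the one that compares arms. Assumptions, none from the documents: compound symmetry; within-person correlation ρ of 0.5 to 0.8; a shift of δ SD at the middle time in the two cuff arms only; no arm difference at baseline or at the end. From the documents: three arms, three times, n = 10-15 per arm, significance level 0.05.

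Centred arm pattern: (1/3, 1/3, −2/3), sum of squares 2/3. Centred time pattern: (−1/3, 2/3, −1/3), sum of squares 2/3. Sum of squared interaction effects = δ² × 2/3 × 2/3 = 4δ²/9. Noncentrality = n × (4δ²/9)/(1 − ρ), with 4 and 2(3n − 3) degrees of freedom.

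| δ | n per arm | ρ | Noncentrality | df | P(significant) |
|---|---|---|---|---|---|
| 0.5 | 10 | 0.5 | 10 × 0.1111/0.5 = 2.22 | 4, 54 | 0.174 |
| 0.5 | 12 | 0.7 | 12 × 0.1111/0.3 = 4.44 | 4, 66 | 0.331 |
| 0.5 | 15 | 0.8 | 15 × 0.1111/0.2 = 8.33 | 4, 84 | 0.597 |
| 0.3 | 10 | 0.5 | 10 × 0.04/0.5 = 0.80 | 4, 54 | 0.090 |
| 0.3 | 15 | 0.8 | 15 × 0.04/0.2 = 3.00 | 4, 84 | 0.232 |

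In the same scenario, a test of the arms on change from baseline to the end stays at its nominal 5%, because the shift is zero at both of those times.

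**Step 4. Does the middle visit cost power for a real end-of-programme effect?** Assumed: end gains of d, d/2 and 0 across the arms, d = 0.8 or 1.0 SD, n = 10 or 15 per arm, ρ = 0.5 or 0.7. If the middle visit shows no change, group-by-time power is 0.31-0.91. If it shows half the gain, as a mid-programme visit might, power is 0.24-0.80. A one-way ANOVA on baseline-to-end change gives 0.31-0.87 whatever happens in the middle. The present timing therefore does not reduce power for the end effect. Moving the visit while relying on the omnibus interaction could cost some, which is a further reason to name the change contrast.

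**The case against.** The strongest reply has four parts.

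**Timing.** A reader might infer that the questionnaires are given immediately, before any daily life or dance. The documents do not say so. Same-day testing is the natural reading, but a visit some days later would also fit. This objection stands. What remains is that the visit follows a single session and that its interval and the recall period are unstated.

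**Expectation.** A reader might infer that the visit measures only expectation. The documents point to other sources. FAAM includes pain, the Experimental Group section says the release work aims to reduce ankle pain, and the Chinese risk description says BFRT may cause fatigue and aggravate pain. A real acute change, in either direction, is possible, and recall of earlier answers would tend to hold scores still. This stands too. But none of these is lasting change in instability or function, and each except recall could plausibly differ by arm.

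**Speed of recovery.** A reader might infer that the trial fails a stated aim. The hope to "improve their rehabilitation speed and effectiveness" appears in the background and Project Summary; the Research Objective names function, strength and range of motion, not speed. So the missing time course is lost information, not an unmet objective.

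**Size and remedy.** The percentages are the power to detect a shift that was assumed, and they do not show that one exists. Moving the visit alone would not prevent the problem either, since a passing mid-programme difference could drive the same test. Both are right, so the remedy has to include a named contrast.

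**Conclusion.** The concern holds in a limited form. CAIT and FAAM are repeated after one session (8.3% to 25% of those planned) and then not until the end. As the protocol describes them, they are poorly placed at that visit to show lasting change. Because no between-group baseline-to-end comparison is named, a transient middle-visit difference could make the group-by-time test significant on its own: 9-23% of trials for an assumed 0.3 SD shift and 17-60% for 0.5 SD. These figures are illustrative and rest wholly on the assumed shift, its confinement to the two cuff arms, its absence by the end, and the assumed correlation structure.

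Net change from baseline to the end is measured and remains usable, and the point does not touch range of motion. Label: cheap improvement.

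**What to change.** 1. After the first session, keep only range of motion, described as an acute-effect measure, and state its interval from the session.
2. Move the middle CAIT and FAAM to a mid-programme session, completed before that session begins, and state the recall period.
3. In Statistical analysis, name the between-group difference in change from baseline to the end of the programme as the main comparison for CAIT and FAAM. The middle score then becomes supportive.
4. Amend Research process and methods (English and Chinese) and Statistical analysis to match. The midpoint can be fixed only once the two conflicting session schedules in Research process and methods are reconciled.

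Cost: the immediate post-session questionnaire score is lost, and questionnaires and range of motion have different middle time points. Assessment occasions rise from three to four, but the added one falls at a session participants already attend, and each questionnaire is still given three times. Naming the contrast costs nothing.

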#### 潜在风险描述

BFRT 干预可能会造成肌肉的疲劳从而加剧疼痛,但是运动强度可控,可以根据实际情况调整

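### The final assessment is timed by intervention received, and the plan does not say that participants who stop training or are re-injured are still measured and analysed as randomised

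*Combined protocol and SAP*

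**What the plan says.** Research process and methods places the CAIT, FAAM and range-of-motion assessments "before intervention, after the first intervention, and after 4 weeks/6 weeks of intervention for the three groups". For strength it says "The ankle strength test was only compared and analyzed at two time points before and after intervention". Statistical analysis repeats the strength schedule with a single duration: "Ankle joint strength was only measured at two time points (before intervention and after 6 weeks of intervention".

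For CAIT, FAAM and range of motion the named analysis is repeated-measures analysis of variance over three time points. For strength, "the data was only analyzed using paired t-tests". No analysis population, withdrawal rule or missing-data method appears anywhere in the document.

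Two sections bear on who might stop. Basic information says that chronic ankle instability raises the "risk of ankle re sprains for patients during walking, exercise, or other activities". The Chinese section on potential risks (潜在风险描述) says "BFRT 干预可能会造成肌肉的疲劳从而加剧疼痛", that is, the training may cause muscle fatigue and so aggravate pain. It adds that intensity is controllable and can be adjusted.

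**The concern.** The last measurement is described by the amount of intervention that precedes it. For someone who stops in week 3, the text does not settle whether a final visit is due. An assessor could see everyone at the end of the programme, or could decide that a person who never completed it has no measurement to take. The plan supports either choice.

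If the second choice is made, the value is not collected and the named tests drop that person. People who stop because of pain or re-sprain are unlikely to be a random subset: those events are poor results for a treatment meant to stabilise the ankle, and CAIT and FAAM should reflect them. The cuff is used in two of the three arms, so losses caused by pain could also differ by arm. A completers-only analysis would then flatter whichever arm lost more of its poor responders.

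**Working it through.** **1. Who has a final value under the plan's wording.** The two sections read side by side:

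- Research process and methods: the final time point is 4 or 6 weeks of intervention for CAIT, FAAM and range of motion, and simply post-intervention for strength.
- Statistical analysis: the final time point is 6 weeks of intervention.
- Neither gives a visit timed from randomisation or from the first session. Neither mentions assessment after stopping.

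**2. What the named tests do with a missing final value.**

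- Paired t-test (strength): needs both values. A person with baseline only contributes nothing.
- Ordinary repeated-measures ANOVA (CAIT, FAAM, range of motion): needs all three values. A person with baseline and the value after the first session is still dropped.

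**3. Possible size.** The plan states no effect size, SD, power or dropout rate, so there is no figure to reproduce. The only usable input is the planned arm size of 10-15 (Research process and methods). Everything else here is assumed: outcome change is normal, there is no true difference between arms, and loss occurs in one arm only.

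If the worst fraction p of an arm is lost, the completers' mean rises by φ(z_p)/(1 − p) SD:

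- p = 0.10: 0.1755/0.90 = 0.195 SD
- p = 0.20: 0.2800/0.80 = 0.350 SD

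If loss has a correlation of only 0.5 with the outcome, multiply by 0.5:

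- p = 0.10: 0.195 × 0.5 = 0.10 SD
- p = 0.20: 0.350 × 0.5 = 0.175 SD

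The illustrative range is therefore about 0.10 to 0.35 SD.

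**4. Cross-check by a second route.** If a share f is lost and those people's mean change is g SD worse than the completers', the completers' mean exceeds the full-arm mean by f × g. With f from 0.10 to 0.30 and g from 0.5 to 1.5, this runs from 0.10 × 0.5 = 0.05 SD to 0.30 × 1.5 = 0.45 SD, which overlaps the range above.

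**5. Scale against the trial's precision.**

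- Twenty per cent of an arm is 0.20 × 10 = 2 to 0.20 × 15 = 3 people.
- The standard error of a difference between two arms, before any loss, is √(2/n): √(2/10) = 0.45 SD and √(2/15) = 0.37 SD.
- The largest illustrative bias, 0.35 SD, is therefore about 0.8 to 0.95 of one standard error. The smallest, 0.10 SD, is about 0.2 to 0.3.

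**The case against.** The best reply is that the document is silent and does not exclude anyone. The assessments are stated for all three groups, and the final time point can be read as a common week-4 or week-6 visit. Project Deadline gives one calendar for everybody, 20/11/2023 to 30/12/2023, which fits a common final date. This reading is possible, and it rules out saying that people who stop do go unmeasured. It does not remove the ambiguity. That calendar is 41 days counting both ends, against 6 × 7 = 42 days for six full weeks, so it leaves no room for someone who pauses to complete six weeks later.

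A reader might also infer that a re-sprained participant would be removed under "Table 1 Inclusion and Exclusion Criteria", because it lists "Acute ankle injury or no joint injury". The documents do not support this. The table sets entry criteria, and no section applies them after randomisation. Read as continuing rules, they would also remove participants whose CAIT score improved past 24. Nor is that row the only one that could be stretched this way: the table also excludes visible injury and inability to comply.

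Three further objections stand in part:

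- **Difference between arms.** The re-sprain risk is described for the condition generally and so applies to every arm. Only the pain sentence points to the blood flow restriction arms, and it goes on to offer adjustment of intensity. Differential loss is possible but not established.
- **Recoverability.** It would be wrong to say that no model can help. CAIT, FAAM and range of motion each have a value after the first session, which a mixed model can use under stated assumptions. Strength has no such intermediate value.
- **Strength.** The planned paired t-test works within an arm. Loss there would distort the within-arm change, not a planned between-arm comparison.

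**Conclusion.** The point holds as an omission that is cheap to repair. The final assessment is tied to intervention received, follow-up after stopping is not provided for, and the named tests drop anyone without a final value. Following the plan as written can therefore give a completers-only result.

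The size is illustrative: about 0.10 to 0.35 SD in favour of the arm with losses, if 10-20% are lost from that arm alone and the loss is related to outcome. No dropout rate, SD or correlation comes from the documents, and similar losses in the other arms would shrink the between-arm bias. A reader might go further and infer that the trial will show a blood flow restriction benefit created by dropout. The documents do not support that, because they neither say that people who stop are left unmeasured nor show that more would stop in those arms.

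**What to change.** 1. **Research process and methods.** Reconcile the 4-6 week and 6 week durations first, since no fixed time can be set until they agree. Then schedule the final CAIT, FAAM, range-of-motion and strength assessments at one fixed time from randomisation or first session, for every randomised participant, whatever training was received. If the physical tests cannot be done, collect at least the CAIT and FAAM questionnaires.
2. **Statistical analysis.** Analyse all participants in their randomised arm. For CAIT, FAAM and range of motion, use a mixed model on all available values, so that a person with a missing final value is retained. Report stops and re-sprains by arm.

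The cost is a few sentences and a few extra visits or calls. The downsides are small: some dilution of the estimated effect because people who stop are included, and some strength values that may still be missing. The change concerns measurement and analysis only; whether an injured participant continues training remains a clinical decision.
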